The objective of this study is to investigate which descriptive patient variables (**exposures**) among 8-19-year-old children and adolescents with self-reported MSK pain (**population**), collected at time of recruitment, are associated to a higher risk of pain (**outcome**) at follow up.

FINER

F	Feasible	-Adequate no. of subjects: 500 -Technical expertise: N/A -Affordable in time and money: Time: short amount of time spent on recruitment per patient and recruitment executed by a GP employee or the GP. Money: a minimum cost per patient, according to rates by The Committee of Multipractice Studies in General Practice. -Manageable in scope: yes
I	Interesting	-Yes, high persistence of youth MSK pain and parental child pain acceptance
N	Novel	-Yes, lack of knowledge of prognostic factors in youth MSK pain and in the setting of general practice
E	Ethical	-Yes, approved by the National Ethics Committee (NVK)(28), without cause for further application.
R	Relevant	-To scientific knowledge: yes. -To clinical and health policy: yes. -To future research: yes.

Methods

Literature search to inform this study

Before commencing the planning of this cohort study, we conducted a systematic literature search to see if other prospective studies had investigated the same research question or were planning to do so. None specifically investigated childhood or adolescent prognostic factors for MSK pain in a general practice setting, nor did any of the included studies find any treatment effect modifiers(14). The systematic review in mention, has now been completed and this cohort study is based on the findings from that review. The prognostic factors found in our review, sparsely covered ethnicity, race, parental income, and residence, which will be investigated in this study. We furthermore limit our patient group to 8-19 years in order to preserve focus on an age group for which only limited knowledge on prognostic factors is available.

Design

This study is a prospective cohort study. We will use the STROBE guideline to report our study findings(29). Below is an illustration of the time line for our study process (figure 1), inspired by the guidelines of Prognosis Research, made by the PROGRESS Group(30). For validation of the prognostic screening, we will use the Transparent Reporting of a multivariable prediction model for Individual Prognosis Or Diagnosis (TRIPOD) Statement(31) and The TRIPOD Explanation and Elaboration document(32) (Appendix 4).

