Reciprocity: A collaborative process of recruitment will take place, where the recruited clinics will contribute with participants and we will present our results to them in return. A short presentation of study results to the clinics will be offered after study completion.

Resolution: A mean number of 3-7 calls is the most effective number, when recruiting(34), why we will adjust and be patient in repeating calls in attempt of a successful recruitment.

Respect: In light of the first authors (NP) profession and clinical experience in GP, aware and respectful towards her fellow GPs work schedule, why participation will not be taken for granted, but appreciated.

Included GP clinics will receive a bulletin paper for display in the waiting rooms of the clinics. This piece of paper will depict concise and short information of the study in different languages, and be used as a recruitment tool. The patient still has to visit the GP, before recruitment in this study. When a patient reads the information written in her mother tongue, she/he will potentially feel that the study is addressing her in a more personal matter, than otherwise when written in a foreign language. The intention of the bulletin is to create curiosity and interest for this study, among patients or relatives at the GPs office. This applies to everyone who knows with a child or adolescent with MSK pain.

Recruitment of participants

The GP is suggested ways of recruitment, in order to choose which best suits the infrastructure of the individual clinic.

Recruitment by an employee:

The employee executes the recruitment process with a screen of all scheduled patients for that day. This prior to the first consultation of the day. The eligibility screening has two criteria: 1. Cause for consultation including a MSK pain complaint and 2. Age 8 to 19 years. The word **MSK** is written next to the names of all eligible patients to indicate and remind the employee or the consulting GP to hand out the questionnaire to the patient, before they leave the clinic.

Not to rarely, is the cause of consultation not mentioned on the schedule. In this case, the words **OBS MSK** is written next to the patients name, notifying the GP of unknown and potential eligibility of recruitment in the study. This, presumed that the patient is 8-19 years old. The GP will screen for eligibility during the consultation with the patient and hand out the questionnaire, if eligible.

Recruitment by the GP:

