The GP screens the schedule for the day, and indicates eligibility with the word **MSK** written next to the patient name.

When consulting a patient with the indicated **MSK**, the GP is reminded to hand the patient the patient material. This can be done, prior, during or in the end of a consultation while the patient is getting dressed.

The patient hands in the completed questionnaire to an employee of the clinic, who stores it in a locked place. NP or her assistant will collect this in agreement with the clinic.

It is also possible for the GP to include a patient if MSK pain comes up during the consultation, without prior mentioning and hence unknown by the employee.

We will recruit patients from September 2018 to December 2019 and expect 500 participants in the ChiBPS cohort. If we are not able to recruit the number of participants according to our sample size calculations recruitment will continue until this number is reached.

Recruitment of parents

The child must first be included in the study in order for his/her parent(s) to be eligible. For included children, we will also request data from parents during a time window of two weeks from the time of Part-Quest receipt. We are not selective as to if and how many of the parents wish to participate. Parents declining participation will not cause withdrawal of the child's eligibility or inclusion.

Contingency plan for recruitment

A tracking data base will be developed to facilitate tracking and accurate reminders to the clinics included. In the process of initial contact with the clinics, a number of expected included participants will be estimated by each clinic. The clinic will make this estimate based on its patient demography,

which can be different across clinics e.g. some clinics will have a majority of young patients and others the opposite. This number will indicate a minimum for successful recruitment.

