Some participants will be anticipated to have poor English and Danish language skills, insufficient to comprehend neither the original English or the Danish questionnaire.

To ensure cross-cultural adaptivity for these participants, we will translate our Danish questionnaires both linguistically and culturally by using professional, hired translators in translation of Danish to Farsi or Danish to Arabic. Translation by experienced authorized translators with not only the target language as their mother tongue, but also familiar with the cultural aspects embedded in the target language.

Persian and Arabic FPS-R are available and will be applied in the Persian and Arabic Part-Quest versions respectively(46).

The questionnaires, will be handed to the participants and their parents in paper. If they are not able to complete the questionnaires while still in the clinical setting (waiting room) and hand them to the secretary when completed, they may at a later point in time (no later than seven days) hand them in at the clinic. Seven days of response time, will be applicable also for follow-up questionnaires, before a reminder is sent out. In contrary to the baseline questionnaire, the follow-up questionnaires will be administered to the participants and parents through e-mail. If for some reason a participant do not respond within the given time limit, he/she will be reminded by e-mail or phone. This will be executed by the assistant, to ensure a satisfactory follow-up rate.

Data management

Retrieved data from both baseline and follow-up participant questionnaires and parent questionnaire will be handled as follows according to the Danish Data Protection Agency(47):

- All personal information is electronic kept in a brief dedicated to the ChiBPS study, on a server owned by Aalborg University (AAU).
- This study will be described in a secure web database, REDCap under AAU server, including who has access to the data and when data is to be deleted.
- To access AAU server and included briefs, a username and password is needed. Only involved researchers will have this access granted. The responsible author NP will store a key file and raw datafiles in a locked brief (passwords to this brief is kept on paper in an envelope in a locked cabinet in her affiliated address, which is also locked, and only researchers with relevant errand has access.

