Appendix 1: Participant Baseline Questionnaire (Part-Quest-baseline)

25. Do you expect to be free of your current pain in the future?

- o Yes, in the near future o Yes, in the long term future o No

26. Why did you come to your doctor today? You may choose more than one answer with circles.

- o I want my pain to stop
 o I am worried about the cause of my pain
 o My family made me come
 o I have a personal problem
 o Because of my pain, I can't use my body as I used to

27. Do you take painkillers, and what do you take? (50)

- o Yes, I take _____ .
 If yes, how often do you take them? _____
 o Yes, I take painkillers, but don't remember the name
 o No, I don't take painkillers

28. Do you expect your doctor to give you medication for your pain?

- o Yes, I would like that
 o No

29. If you have a job, how would you generally describe your physical activity in your job? (56) Please choose one.

- o Mostly sedentary work that does not require physical exertion
 o Mostly standing or walking work, which otherwise does not require physical exertion
 o Standing or walking work with some lifting or carrying work
 o Heavy or fast work which is physically strenuous
 o I don't have a job
 o I don't know

In the following last questions mark "x" in yes or no

[figure not shown]
[figure not shown]
	Yes	No
Is your pain radiating to your legs or arms(40)?		
Do you feel anxious(57)?		
Do you think that you have low self-esteem(57)?		
Do you believe in God?		
Is it difficult to fall asleep because of pain(44)?		
Is it difficult to sit during a lesson(44)?		
Does your pain disturb a walk longer than 1 km(44)?		
Does your pain disturb your physical exercise(44)?		
Does your pain disturb your hobbies(44)?		
Do you have pain outside school hours?		
Are you tired during the day(16)?		
Do you feel depressed(44, 57)?		

Does your pain make any of the following activities difficult(40)?	Yes	No
-reaching up to get a book from a high shelf		
-carrying your school bag to school		
-sitting on a school chair for a 45 min. lesson		
-standing in a queue for 10 min		
-sitting up in bed from a lying position		
-bending down to put your socks on		
-standing up from an armchair at home		
-running fast to catch a bus		
-sport activities at school		

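### Part-Quest-baseline may be completed before, during or up to seven days after the GP consultation, and the printed form records neither the date nor whether the doctor had been seen

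*Protocol*

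**What the plan says.** The objective treats the exposures as "collected at time of recruitment".

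The timing of the baseline form is described in three places:

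- *Recruitment by an employee*: a mark on the day's schedule serves to "remind the employee or the consulting GP to hand out the questionnaire to the patient, before they leave the clinic". If the reason for the visit is not on the schedule, the GP screens during the consultation and hands out the form then.
- *Recruitment by the GP*, on handing over the material: "This can be done, prior, during or in the end of a consultation while the patient is getting dressed". The GP may also include a patient whose pain first comes up in the room.
- The administration paragraph at the end of *Translation of questionnaires*: patients who cannot finish in the waiting room are told "they may at a later point in time (no later than seven days) hand them in at the clinic".

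The procedure is left to the clinic: "The GP is suggested ways of recruitment, in order to choose which best suits the infrastructure of the individual clinic".

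Appendix 1 asks about expected recovery (item 25), painkillers taken (item 27) and, in item 28, "Do you expect your doctor to give you medication for your pain". Items 5 and 6 ask about the past two weeks. As printed, the form has no completion date and no before/after mark. Under *Statistical methods*, the stated guard against information bias is that all patients get identical questionnaires.

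**The concern.** A baseline value should mean the same thing for every participant. Item 28 is worded as though the consultation lies ahead; once the visit is over, the answer may simply report what the doctor did. Item 25 can shift with a diagnosis or reassurance, and item 27 could pick up a painkiller started at the visit. If some participants answer before and others after, one coefficient is estimated from two different measurements.

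Because clinics choose the route, the mix can also differ by clinic, so timing may go along with differences in patients or practice. Identical wording does not guard against this. An analysis plan cannot repair it either if timing was never recorded.

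**Working it through.** The plan states no figure on this point, so there is none to reproduce. The check sets the passages side by side and adds one ratio.

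**Step 1: which completion times does the text allow?**

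| Route | Earliest hand-out | Latest return |
|---|---|---|
| GP route, patient marked on the schedule | before the consultation | seven days later |
| Employee route, reason for visit known | any time before leaving the clinic | seven days later |
| Reason for visit not on the schedule | during the consultation, after GP screening | seven days later |
| Pain first mentioned in the room | during the consultation | seven days later |

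The last two rows cannot give a form completed wholly before the consultation; the first two can. The protocol says that a missing reason for the visit is not rare. Mixed timing is therefore built into the procedure and does not depend on clinics departing from it.

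**Step 2: can the two kinds of answer be separated later?** Appendix 1 ends each page with name, phone and e-mail fields but shows no date and no before/after item. Completed forms are stored at the clinic and collected later, so the collection date is not the completion date. *Recruitment of parents* starts a two-week window when the participant form is received, so some receipt date may exist. That would identify late returns, but not whether a form handed in on the day was completed before or after seeing the doctor.

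**Step 3: how far can the two-week window shift?** Inputs: a delay d of 0 to 7 days (administration paragraph, counted here from the day of the visit, which is an assumption) and a recall window of 14 days (items 5 and 6). Share of the window after the visit = d / 14.

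- d = 0: 0/14 = 0%
- d = 1: 1/14 = 7%
- d = 3: 3/14 = 21%
- d = 7: 7/14 = 50%

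The last line is the extreme for a form completed on the last permitted day. It is a shifted window, not an estimate of bias.

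**Step 4: which items are exposed?**

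- Most sensitive: items 28 and 25, and possibly 27.
- Shifted window: items 5 and 6.
- Little affected: stable items such as height, siblings and country of birth, and most of the exposures numbered under *Outcomes*, which ask about usual or current state (for example usual episode length and frequency, or activities made difficult by pain).

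**Step 5: can bias in the odds ratios be computed?** No. That needs the share of forms completed after the visit and the effect of the visit on the answers. The protocol gives neither.

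**The case against.** Several points on the other side stand and limit the conclusion.

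- *The order of events.* A reader might infer that the protocol contradicts itself, because it also says "The patient still has to visit the GP, before recruitment in this study". That sentence belongs to the paragraph on the waiting-room bulletin and means only that reading the notice does not recruit anyone. The eligibility section lists three time-points: schedule screening, consultation and a later phone call. Early hand-out with later confirmation fits that. The text allows flexible timing; it is not shown to be contradictory.
- *Contamination.* A reader might infer that the exposures are spoiled, or that an effect of expectation would merely reflect the GP's reassurance. The objective is association with later pain, and it asks for exposures at recruitment, not before the consultation. An expectation held after the visit can be a valid prognostic factor. The problem is mixed and unrecorded timing.
- *Reach.* Items 25, 27 and 28 are not in the numbered exposure list, nor among the factors used for the sample size. The *Questionnaires* section suggests that questionnaire items in general are candidate factors, so these items are exploratory but not irrelevant. The item asking why the patient came that day is in the past tense and can be answered after the visit.
- *Remedy.* A reader might want every form completed on arrival. That would have minors fill in an identifiable form before eligibility and custody-holder consent are settled. It would also include patients whose visit has nothing to do with musculoskeletal pain, and it would override flexibility that the protocol offers clinics on purpose. Rewording items to ask what was expected before the visit would add recall error. Neither is needed.

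What these points do not answer is that before and after answers on the same day cannot be told apart once the forms are in.

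**Conclusion.** The point holds in a limited form. The protocol permits baseline completion on either side of the consultation, by a route that each clinic chooses, and the form as printed does not record which applied. Items 28 and 25, and possibly 27, can be affected in some participants and not in others. For the two-week items, 0% to 50% of the window can fall after the visit. Whether this occurs often, and how large or in which direction any bias would be, cannot be determined from the document; any figure for the number of participants affected would be a guess.

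This rests on two assumptions: that the seven days run from the visit, and that no date or timing field sits on a part of the form that is not visible. The main listed exposures and the general design are not called into question. The omission still matters because timing that is not recorded at completion cannot be recovered by later analysis.

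**What to change.** 1. Add two fields to page 1 of Part-Quest-baseline: *Date completed* and *Completed before / after seeing the doctor*.
2. In both recruitment routes and in the paragraph on returning questionnaires, state that baseline may be completed before or after the consultation and that the timing is recorded.
3. Report the associations of items 25 and 28 (and 27 if it is used as a factor) by completion status, or adjusted for it. Separate estimates are more informative, because adjustment alone still assumes that the item means the same in both groups. As clinics choose the route, say that completion status may partly stand for clinic.

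The cost is two extra fields, a sentence in each place and one sensitivity analysis, whose subgroups will be smaller and less precise than the full cohort. Clinic workflow, consent order and item wording stay as they are. The fields need to be on the form from the first participant; forms completed without them cannot be classified later.

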With our primary outcome we aim to capture pain that interferes with their everyday lives and collect the location of pain. The patient characteristics (exposures) are based on results from our systematic review(14), used in other studies (when including references).

The specific wording in the outcomes and throughout the questionnaire has been pilot tested among similar aged kids and adolescents.

Our secondary outcomes highlight the development or potential aggravated psychological and social factors related to musculoskeletal pain at follow-up.

Primary outcome

1) MSK pain influence

Q: Have you experienced pain in the past two weeks that have lead you to not being able to participate in play in the school yard or sparetime activities (ex. football or other sparetime activity)(38)?

If yes, we ask them to draw the area where they have experienced this pain with the following question:

Q: Draw on your body the areas you have had pain during the past two weeks (39).

These two questions will form our primary outcome and will be collected at all endpoints.

Secondary outcomes

1) Problemfilled MSK pain.

*Q: Draw a circle around the area of your body, where you have had the **most** problems with pain. You may only draw **one** circle.*

2) Pain intensity depicted on Faces Pain Scale Revised (FPS-R) or a 10 cm VAS scale for 8-11 and 12-19 year olds respectively (9).

Exposures

3) Self-reported anxiety.

Q: "Do you feel anxious"?

4) Self-reported depression (16).

Q: "Do you feel depressed"?

5) Self-reported low self-esteem (16).

Q: "Do you think that you have low self-esteem"?

6) Duration of troublesome pain episode (40, 41).

Q: "How long does a pain episode usually last"? (see appendix 1 and 2 for the Q in full length).

7) Frequency of troublesome pain episode (10, 42, 43).

Q: "How often do have a pain episode"? (see appendix 1 and 2 for the Q in full length).

8) Nervousness (41).

Q: "How often do you feel nervous"? (see appendix 1 and 2 for the Q in full length).

9) Higher disability index (12, 44).

Q's with yes/no answers:

1. is it difficult to fall asleep because of pain?

2. is it difficult to sit during a lesson?

3. does your pain disturb a walk longer than 1km?

4. does your pain disturb your physical exercise?

5. does your pain disturb your hobbies?

10) Higher HFAQ level (40).

Q: "Does your pain make any of the following activities difficult"?

1. reaching up to get a book from a high shelf

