Appendix 1: Participant Baseline Questionnaire (Part-Quest-baseline)

1. Is this your first consultation with your general practitioner concerning your current musculoskeletal pain condition? Mark one answer.

Yes No, this is consultation number _____ with my current musculoskeletal pain condition

[figure not shown]
2. Draw a circle around the stage of your current physical features. Girls draw on the right figure and boys on the left.

3. How tall are you? _____ cm

4. How much do you weigh? _____ kg

Below is a drawing of **your** body.

5. Draw on your body the areas you have had pain or it has hurt, during the past two weeks. If you haven't felt hurt or pain during the past two weeks or currently, please write X here _____ (50)

6. Have you felt hurt during the past two weeks leading to not being able to participate in play in the school yard or sparetime activities (ex. football or other sparetime activity)? yes _____ no _____

7. Draw a circle around the area of your body, where you have had the **most** problems with pain. You may only draw **one** circle.

8. Mark the statements below, that are true about your pain. You may mark more than one.

[figure not shown]
- it can easily be ignored
- it affects my concentration
- sometimes I have to take pain medication
- sometimes I can't attend school because of the pain.

If you are 8 to 11 years old, please answer question 9.

If you are 12 to 19 years old, please *skip* question 9 and answer question 10.

9. These faces show how much something can hurt.

This face shows no pain.

The faces show more and more pain up to this one – it shows very much pain. Circle the face that shows how much you hurt (46).

10. On a scale of 0 to 10, where 0 is no pain and 10 is the worst possible pain, circle the number that best represents your pain (9).

0 1 2 3 4 5 6 7 8 9 10

Your name _____ Your phone no. _____ Your e-mail _____ 13

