Appendix 2: Participant follow-up Questionnaire (Part-Quest-Follow-up)

1. How many consultations have you had with your general practitioner concerning your current musculoskeletal pain condition during the last 3 months(/3 months/6 months at respectively first, second, and third follow-up questionnaires)? _____

[figure not shown]
2. Draw a circle around the stage of your current physical features. Girls draw on the right figure and boys on the left.

3. How tall are you now? _____ cm

4. How much do you weigh now? _____ kg

Below is a drawing of **your** body.

5. Draw on your body, the areas you have had pain or it has hurt, during the past two weeks. If you haven't felt hurt or pain during the past two weeks or currently, please write X here _____

6. Have you felt hurt during the past two weeks leading to not being able to participate in play in the school yard or sparetime activities (ex. football or other sparetime activity)? ? yes _____ no _____

7. Draw a circle around the area of your body, where you have had the **most** problems with pain. You may only draw **one** circle.

[figure not shown]
8. Draw circles around the statements that are true about your pain. You may choose more than one statement.

- it can easily be ignored
- it affects my concentration
- sometimes I have to take pain medication
- sometimes I can't attend school because of the pain

If you are 8 to 11 years old, please answer question 9.

If you are 12 to 19 years old, please *skip* question 9 and answer question 10.

9. These faces show how much something can hurt.

The faces show more and more pain up to this one – it shows very much pain. Circle the face that shows how much you hurt.

10. On a scale of 0 to 10, where 0 is no pain and 10 is the worst possible pain, circle the number that best represents your pain (9).

0 1 2 3 4 5 6 7 8 9 10

Your name _____ Your phone no. _____ Your e-mail _____ 16

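### The primary outcome promises the location of the activity-limiting pain, but no questionnaire item asks for it, and the activity question is not limited to musculoskeletal pain

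*Protocol*

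**What the plan says.** The Outcomes section of the protocol aims to capture pain that interferes with daily life and to record where it is. The primary outcome, labelled MSK pain influence, has two parts.

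- Activity question: "Have you experienced pain in the past two weeks that have lead you to not being able to participate in play", continuing with the school yard and spare-time activities.
- Drawing: "If yes, we ask them to draw the area where they have experienced this pain with the following question". The question printed next is "Draw on your body the areas you have had pain during the past two weeks".

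The section closes: "These two questions will form our primary outcome and will be collected at all endpoints".

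The questionnaires print these items differently. In Appendix 1, item 5 reads "Draw on your body the areas you have had pain or it has hurt, during the past two weeks", and in Appendix 2 "Draw on your body, the areas you have had pain or it has hurt, during the past two weeks". Both are put to every child, with an X for no pain, and both come before the activity question. That question is item 6, "Have you felt hurt during the past two weeks leading to not being able to participate", answered yes or no, with no drawing attached to a yes. Item 7 begins "Draw a circle around the area of your body, where you have had the" and asks for a single circle where pain has been most troublesome. The protocol lists item 7 as a secondary outcome.

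**The concern.** The protocol means to tie a body area to the pain that stopped the activity, but nothing it prints does so. If a child answers yes and draws only a knee, the site can reasonably be inferred. If the child draws a knee and the abdomen, it cannot, and item 7 is only a partial tie-break, because the area with most problems need not be the one that stopped the activity.

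Neither version of the activity question is restricted to musculoskeletal pain. A child whose knee still aches a little, but who missed football because of abdominal pain, truthfully answers yes and draws a musculoskeletal area. That child counts as an event for a reason outside the outcome's label.

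False events that are equally common at both levels of a prognostic factor pull its odds ratio toward 1. If they are more common at one level, they can move it in either direction. The Sample-size section names multisite pain as a prognostic factor, and children with several painful areas are the ones whose limiting site is ambiguous. An unequal share is therefore plausible for that factor, though the document does not quantify it.

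**Working it through.** **Step 1: which item could locate the limiting pain?**

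| Item | Asked of | What it locates |
|---|---|---|
| Drawing question in the Primary outcome section | Those answering yes, per the lead-in | All areas painful in two weeks |
| Item 5, Appendices 1 and 2 | Every child, before item 6 | All areas painful or hurting in two weeks |
| Item 6, Appendices 1 and 2 | Every child | Nothing (yes or no) |
| Item 7, Appendices 1 and 2 | Every child | One area with most problems |

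No row locates the pain that stopped the activity. The section on baseline data says that the questionnaires cover all assessments without exception, so no other instrument supplies the link.

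**Step 2: is the event limited to musculoskeletal pain elsewhere?** The definition of musculoskeletal pain and the excluded causes stand under Eligibility criteria. They apply at entry, and no matching rule is stated for the follow-up outcome.

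**Step 3: how far could an odds ratio move?** The plan has no figure of its own here, so this is an illustration.

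Inputs from the protocol: odds ratio 1.78 for female sex (interval 1.18 to 2.69) and a female share of 0.5 (Appendix 5); 50% with pain at follow-up and 480 participants before allowance for loss (Sample-size). The 50% is stated for continuing pain, not for activity-limiting pain, so an assumed 30% is shown as well.

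Assumed: a share f of true non-cases still counted as events after the drawing has been used, f = 1% to 7.5%.

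True risks: solve (p0 + p1)/2 = m with p1/(1 − p1) = 1.78 × p0/(1 − p0), where 0 is boys and 1 is girls.

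- m = 0.50: p0 = 0.4284, p1 = 0.5716.
- m = 0.30: p0 = 0.2401, p1 = 0.3599.

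Observed risk: q = p + (1 − p) × f. Example with m = 0.50 and f = 0.075: q0 = 0.4284 + 0.5716 × 0.075 = 0.4713; q1 = 0.5716 + 0.4284 × 0.075 = 0.6037. The odds are 0.8914 and 1.5234, and their ratio is 1.71.

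| f in boys | f in girls | OR at 50% events | OR at 30% events |
|---|---|---|---|
| 1% | 1% | 1.77 | 1.76 |
| 2.5% | 2.5% | 1.75 | 1.72 |
| 5% | 5% | 1.73 | 1.67 |
| 7.5% | 7.5% | 1.71 | 1.63 |
| 2.5% | 7.5% | 1.92 | 1.97 |
| 7.5% | 2.5% | 1.56 | 1.43 |

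The last two rows assume a threefold difference by sex, for which the documents give no evidence. They show direction only.

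In children, at 50% events there are 480 × 0.5 = 240 true non-cases, so 1% to 7.5% is about 2 to 18 children. At 30% there are 480 × 0.7 = 336, so about 3 to 25.

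**The case against.** The strongest reply is that the drawing is already half of the primary outcome. Once it is used, an error needs three things in one child: non-musculoskeletal pain that stopped activity within two weeks, a musculoskeletal area drawn as well, and that musculoskeletal pain not itself limiting. Coding of drawings is ordinary SAP content, and the protocol announces a SAP that is not shown here. Participants enter because of musculoskeletal pain, the follow-up form opens by referring to that condition, lay wording suits children from age 8, and the protocol says the wording was pilot tested.

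Most of this stands as an argument about size, and it is why only residual error is modelled above. It does not remove the point. A SAP can say how drawings are coded, but it cannot supply a link that the child was never asked for. The opening reference to the condition frames the form without restricting item 6.

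A reader might also infer three stronger things that the documents do not support.

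- That every non-musculoskeletal yes passes straight into the outcome. It does not, because the drawing belongs to the outcome and can largely settle the matter when a single area is drawn.
- That the objective, which says only pain, contradicts the PEO table, which says MSK pain. The table leads directly into the objective, so the shorter word reads as shorthand.
- That asking the drawing before the activity question loses data. Every child is asked to draw, so no drawing is lost. The order, and the choice between felt hurt and experienced pain, are points of harmonisation.

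**Conclusion.** The point holds. The stated primary outcome and the printed items disagree, and for children who draw more than one area the site of the limiting pain cannot be recovered. Some events may therefore not be musculoskeletal.

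The size is unknown from the documents and probably small. With equal residual shares of 1% to 7.5%, the shift is from 1.78 to no lower than 1.71 at 50% events and 1.63 at 30%. A share that differs by factor could move an odds ratio up or down. All the illustrated values lie inside the protocol's own interval for sex, 1.18 to 2.69. This is a modest bias in a primary outcome, worth correcting because the correction is cheap. The documents do not support a claim that a finding would reverse or that the outcome is unusable.

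**What to change.** In the Primary outcome section and in Appendices 1 and 2, use one wording and one order. After a yes to item 6, ask the child to mark the area or areas of the pain that stopped the activity. Keep item 5 as a separate any-pain drawing. Define the primary event as a yes plus at least one marked musculoskeletal region, coded by the study team so that children need not judge tissue origin. State plainly that a marked region shows site and not cause: a marked knee or back cannot rule out the causes excluded at entry.

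The cost is one extra drawing for those who answer yes, matching edits to the Danish, Farsi and Arabic versions, and a short re-pilot. No visits or participants are added.

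If data collection has already started, leave the forms unchanged so that baseline and the 3-, 6- and 12-month answers stay comparable. Instead, prespecify a sensitivity analysis that screens events by the sites drawn in items 5 and 7, and report it as a partial remedy.
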